17.0 Pharmacodynamic Analysis

Based on nonclinical and clinical studies conducted with HFA-152a, and information from the Summary of product characteristics (SmPC) of Ventolin Evohaler (salbutamol sulfate containing propellant HFA-134a), the safety concerns following salbutamol dosing at the levels employed in this study include hypokalemia, hyperglycemia, and cardiovascular effects (including tachycardia and, in rare cases, cardiac arrhythmias).

The analysis of potassium in serum samples will be performed at CCI

Heart rate and QTcF data used for PD parameters will result from the 12-Lead ECG measurements as part of the safety measurements.

17.1 Pharmacodynamic Variables

17.1.1 Variables

17.1.1.1 Serum Potassium, Heart Rate and QTcF

- Serum potassium.

Heart rate and QTcF results will be reported as safety assessments, see Section 18.1.5. Additional parameters will be part of the PD assessments, see section 17.1.1.2.

17.1.1.2 Parameters

PD parameters for serum potassium, heart rate and QTcF will be calculated as defined in Table 4, as data permit.

Table 4 PD Parameters for Serum Potassium, Heart Rate and QTcF

Parameter	Description	SAS Programming Notes
Emin, K	Minimum observed serum potassium	Minimum observed concentration after dose (pre-dose not included)
AUEC, K	Weighted mean serum potassium (0-4 hr).	Summation of each interval, each interval calculated as: (C2-C1)/2 * (t2-t1), where C2 and t2 are concentration and timepoint at the end of each interval, and C1 and t1 are concentration and timepoint at the start of each interval.
Emax, HR	Maximum observed heart rate	Maximum observed heart rate after dose (pre-dose not included)
AUEC, HR	Weighted mean heart rate (0-4 hr).	Summation of each interval, each interval calculated as: (C2-C1)/2 * (t2-t1), where C2 and t2 are heart rate and timepoint at the end of each interval, and C1 and t1 are heart rate and timepoint at the start of each interval.
Emax, QTcF	Maximum observed QTcF	Maximum observed QTcF after dose (pre-dose not included)
AUEC, QTcF	Weighted mean QTcF (0-4 hr).	Summation of each interval, each interval calculated as: (C2-C1)/2 * (t2-t1), where C2 and t2 are QTcF and timepoint at the end of each interval, and C1 and t1 are QTcF and timepoint at the start of each interval.

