8.11.3. PD blood sampling

For PD blood samples, pre-dose samples will be obtained between waking up and dosing. Post-dose samples up to 30 minutes post-dose will be obtained with a time window of ± 2 minutes. Thereafter, post-dose samples will be obtained with time margins of $\pm 5\%$ of the time that has passed since (last) dosing.

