4.0 Changes from Previous Version of Approved SAP

This is the second version of the SAP. Changes from the first SAP version:

- Public disclosure tables have been added.
- Additional imputation rules for partial dates have been added for AEs.
- Sections of statistical analysis on PK and PD parameters have been changed slightly to allow for data driven model modifications. In addition, participants with parameter results for only one treatment will no longer be excluded from the statistical analyses.
- Descriptive statistics for routine urinalysis has been added.
- Headline summary PK TFLs as a separate deliverable and dry-run delivery have been removed.

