5.5 Secondary Estimand (2)

The clinical question of interest is for the secondary objective: What is the geometric mean ratio (GMR) of the PD parameters of Salbutamol HFA-152a MDI vs Salbutamol HFA-134a MDI after administration of single doses of salbutamol in healthy participants.

- **Population:**

Healthy male or female participants aged 18 to 55 years

- **Endpoints:**

- Minimum and 0-4h weighted mean serum potassium
 - Maximum and 0-4h weighted mean heart rate
 - Maximum and 0-4h weighted mean QTc interval

- **Treatment conditions:**

Salbutamol will be administered as a single 800 µg dose, given as 8 actuations each separated by a 20-second interval, each delivering 100 µg as the ex-valve dose for the test treatment and a reference treatment.

The comparison of interest is: The ratio of Salbutamol HFA-152a MDI vs Salbutamol HFA-134a MDI .

- **Intercurrent events:**

- **Treatment discontinuation due to any reasons - hypothetical strategy**

- Interest lies in the comparisons of ratio of formulations in a hypothetical scenario where no participant discontinued from the study. The individual PD concentrations affected by occurrence of the intercurrent event would be treated as missing from the occurrence of the intercurrent event until the end of the study and consequently affected individual PD parameters will be missing.

- **Occurrence of emesis or coughing on dosing - Hypothetical strategy**

- Interest lies in the comparisons of the ratio of formulations in a hypothetical scenario where no participant experiences an episode of coughing or emesis within a treatment that is judged by the investigator to have impacted inhaled drug delivery to the airways or swallowed drug absorption from the gastrointestinal tract. The individual PD concentrations affected by occurrence of the intercurrent event would be treated as missing from the occurrence of the intercurrent event until the end of the treatment (period) and consequently affected individual PD parameters will be missing for that treatment (period).

- **Dosing error: Considered less than or more than prescribed dose - Hypothetical strategy**

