17.2.2 Pharmacodynamic Parameters

PD parameters will be calculated in SAS.

Actual times, rather than scheduled sampling times, will be used in all computations involving timepoints, except for pre-dose timepoint. Pre-dose timepoints will be set to zero.

Descriptive statistics (number of participants, arithmetic mean, SD, CV, geometric mean, median, min, and max) will be used to summarize the calculated PD parameters by treatment. For Emax and Emin, only median, min and max will be presented.

Participants excluded from the PD analysis set will be flagged in the listing and excluded from descriptive statistics.

All individual participant serum potassium parameters, heart rate and QTcF parameters will be listed.

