17.2.2.1 Statistical Analysis of Pharmacodynamic Parameters

Analysis will be performed to compare the PD parameters after dosing of salbutamol HFA-152a MDI and salbutamol HFA-134a MDI (currently marketed Ventolin product). Analysis will be performed on the natural logarithm of Emin and AUEC of serum potassium, and EMax and AUEC of heart rate and QTcF, using a linear mixed model with the treatment and period (dosing day) as fixed effects and subjects as random effects. A one model will be used, grouped by parameter.

Point estimates and 90% CIs for treatment differences on the log scale derived from the model will be exponentiated to obtain estimates for geometric mean (GM) ratios and CIs on the original scale. The within-subject coefficients of variation (CVw) for AUEC, Emin and Emax will be calculated based on the loge-normal distribution.

Model Checking & Diagnostics:

- Model assumptions will be checked before analysis.
- The underlying distributional assumptions involved in the statistical analyses will be assessed by visual inspection of residual plots. Normality will be examined by normal probability plots while homogeneity of variance will be assessed by plotting the residuals against the predicted values for the model.
- If the assumptions are seriously violated, then alternative data transformations will be explored. If no suitable transformation can be found, equivalent nonparametric analyses (ex. Wilcoxon signed-rank test) will be performed.

The following kernel code of SAS PROC MIXED will be used:

```
proc mixed;  
  by parameter;  
  class subject treatment period;  
  model log(value)= treatment period / ddfm=kenwardroger cl;  
  random subject /type=un;  
  lsmeans treatment period /alpha=0.1;  
  /*estimates for treatment order Test1-Ref*/  
  estimate "T vs R" treatment 1 -1 /alpha=0.1;  
run;
```

SAS code might be updated depending on the data. An unstructured type of the covariance matrices R (accounting for the within subject variability) and G (accounting for the between subject variability) will be used. If this model fails to converge, alternative covariance structures may be considered based on a lower AIC values (for example variance component, etc.). For the described linear mixed model analyses, the Kenward and Roger method for approximating the denominator degrees of freedom and correcting for bias in the estimated variance-covariance of the fixed effects will be used.

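### SAP Table 4 subtracts instead of adding in the 0-4 h weighted means, so three of the six PD endpoints do not measure a mean level and often cannot be log-transformed

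*SAP*

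**What the plan says.** The PD estimand (SAP section 5.5) names "Minimum and 0-4h weighted mean serum potassium" as endpoints, and pairs a maximum with a 0-4 h weighted mean for heart rate and for QTc. That makes six endpoints, three of them weighted means.

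Table 4 in SAP section 17.1.1.2 calls the potassium parameter AUEC and describes it as "Weighted mean serum potassium (0-4 hr"). The SAS Programming Notes column then gives the calculation: "Summation of each interval, each interval calculated as: (C2-C1)/2 * (t2-t1"). C1 and t1 are the value and time at the start of the interval, C2 and t2 those at its end. The heart-rate and QTcF rows repeat the same formula. None of the three rows divides by elapsed time.

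Section 17.2.2 adds "Actual times, rather than scheduled sampling times, will be used in all computations involving timepoints", with pre-dose set to time zero. Section 17.2.2.1 states: "Analysis will be performed on the natural logarithm of Emin and AUEC of serum potassium, and EMax and AUEC of heart rate and QTcF". The treatment effect is a ratio of geometric means with a 90% CI. No other part of the protocol or SAP gives a different formula; Protocol section 9.3.3 refers only to weighted means.

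**The concern.** The area of a trapezoid is the average of its two sides times its width. Table 4 takes half the difference of the sides times the width. That quantity depends on how the profile rises and falls, weighted by interval length, and not on where the profile lies.

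Three things are at stake.

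- The reported ratio would estimate something other than a ratio of weighted means, and it can point the wrong way.
- Any zero or negative value drops out of a model fitted to logarithms, and whether it drops out depends on the outcome itself. A participant with one usable period stays in, because "participants with parameter results for only one treatment will no longer be excluded from the statistical analyses" (SAP section 4.0).
- These endpoints carry the between-propellant comparison of the effects that SAP section 17.0 itself names as safety concerns: hypokalemia and cardiovascular effects.

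The missing division is a lesser fault. If every profile ended at exactly 4 h it would cancel from the treatment ratio. With actual times it does not.

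**Working it through.** **Inputs from the documents.** PD blood samples and ECGs are scheduled pre-dose and at 0.25, 0.5, 1, 1.5, 2 and 4 h (Protocol section 1.3, footnotes e and g). The interval lengths d are therefore 0.25, 0.25, 0.5, 0.5, 0.5 and 2 h. The plan states no AUEC value, so there is no figure of its own to reproduce.

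**Weight on each observation.** Collecting terms, an interior observation receives (d before - d after)/2 under the written rule and (d before + d after)/2 under the trapezoid. The first and last observations receive -d/2 and +d/2 under the written rule, and +d/2 each under the trapezoid.

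| Time (h) | 0 | 0.25 | 0.5 | 1 | 1.5 | 2 | 4 | Sum |
|---|---|---|---|---|---|---|---|---|
| As written | -0.125 | 0 | -0.125 | 0 | 0 | -0.75 | +1 | 0 |
| Trapezoid | 0.125 | 0.25 | 0.375 | 0.5 | 0.5 | 1.25 | 1 | 4 |

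Each interval adds +d/2 and -d/2, so the written weights sum to zero at any set of times, scheduled or actual. On the scheduled times, the 15 min, 1 h and 1.5 h values get no weight at all.

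**Illustrative profiles.** The values are assumptions; the documents give none.

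| Profile at the seven times | As written | True weighted mean |
|---|---|---|
| K 4.2, 4.0, 3.8, 3.7, 3.7, 3.8, 4.0 | 0.15 | 15.4/4 = 3.85 |
| Same, all values 0.4 lower | 0.15 | 3.45 |
| Same, fall from baseline 50% deeper | 0.225 | 3.675 |
| HR 62, 70, 72, 71, 69, 68, 64 | -3.75 | 271.25/4 = 67.8 |
| HR 62, 64, 66, 68, 70, 70, 70 | +1.5 | 68.75 |
| QTcF 405, 410, 413, 412, 411, 410, 407 | -2.75 | 409.75 |
| QTcF 405, 406, 408, 410, 411, 412, 412 | +1.4 | 410.7 |

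For example, the first potassium score is -0.125 × 4.2 - 0.125 × 3.8 - 0.75 × 3.8 + 4.0 = 0.15.

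**Effect on the ratio.**

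- Uniform lowering by 0.4: written 0.15/0.15 = 1.00; true 3.45/3.85 = 0.896.
- Fall 50% deeper: written 0.225/0.15 = 1.50; true 3.675/3.85 = 0.955.

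**How often the logarithm is undefined.** With independent normal errors of standard deviation SD at each time, the score has standard deviation SD × sqrt(0.125² + 0.125² + 0.75² + 1²) = 1.2624 × SD. The share of period values at or below zero is Phi(-score/(1.2624 × SD)).

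| Variable | Assumed SD | Share at or below zero |
|---|---|---|
| Potassium | 0.1 to 0.3 | 0.3% to 79% |
| Heart rate | 3 to 8 | 35% to 84% |
| QTcF | 5 to 12 | 41% to 67% |

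The heart-rate and QTcF ranges use the profiles above. The potassium range uses the first profile, the same profile with a 4 h value of 4.2, and 4.2, 4.0, 3.8, 3.7, 3.6, 3.6, 3.6. For the first potassium profile at SD 0.2 the share is Phi(-0.15/0.2525) = 28%. If the two periods are independent, 0.28² = about 8% of participants lose both.

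**Missing division, once the sign is corrected.** The reported mean would be about four times too large (15.4 instead of 3.85). For potassium, Protocol section 8.11.3 says "Thereafter, post-dose samples will be obtained with time margins of" ±5% of elapsed time, so the 4 h sample may fall at 3.8 or 4.2 h. The first potassium area is then 14.62 or 16.18, a shift of 5.1%. For the ECG variables, SAP section 17.0 says "Heart rate and QTcF data used for PD parameters will result from the 12-Lead ECG measurements as part of the safety measurements", which suggests the ±10% safety window of Protocol section 8.11.4. At 3.6 or 4.4 h the first heart-rate area is 244.85 or 297.65, a shift of 9.7%. After division by actual elapsed time, the largest shift in the profiles above is 0.3%. These are window edges, not expected deviations.

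**The case against.** The best reply is that this is an evident slip with one possible reading. The same rows call the parameter a weighted mean, so any programmer would know what is meant. Datasets are double programmed (SAP section 9.2.4) and individual PD parameters are listed, so a mean heart rate of -3.75 would hardly pass unseen. Programming may begin before lock (SAP section 8.2), the code may be updated, and other transformations or a nonparametric analysis are allowed if assumptions fail (SAP section 17.2.2.1). SAP section 3.0 also lets changes go into the CSR without a new SAP version. Restoring a plus sign to match a named endpoint leaves little room for bias. The endpoints are secondary and no formal hypothesis is tested.

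Much of this stands. Detection is likely, a late correction would not be a free choice, and loss of non-positive values is the result of the printed code rather than the only route open. The wide ranges above show that undefined logarithms can be common; they do not predict how common.

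It does not rescue the text. The formula is in the programming specification, and two programmers working from it can agree on the same wrong number. Another transformation or a rank test would still analyse the wrong quantity. Programming and its quality control are completed only after lock, draft tables come after lock (SAP section 7.2), the dry run has been removed (SAP section 4.0), and the randomization code is also released after lock (SAP section 6.2). A correction made then departs from the signed plan at a time when the treatment codes may be known. A misreading of the PDF is unlikely: the minus sign appears in all three rows, while plus signs survive elsewhere in the SAP.

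**Conclusion.** The concern holds, and the formula must be corrected. As written, the three AUEC parameters ignore the level of potassium, heart rate and QTcF, so their geometric mean ratios are wrong or undefined. That conclusion follows from the formula alone and needs no assumption about the data. The numerical examples rest on assumed profiles, and the shares of unusable values also on assumed SDs and independent normal errors. The omitted division is secondary: it puts the parameter on the wrong scale and, with actual times, adds avoidable timing noise to the ratio. The damage is confined to three secondary PD endpoints.

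**What to change.** In all three AUEC rows of Table 4, replace the formula with:

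weighted mean = SUM[(C1 + C2)/2 × (t2 - t1)] / (t_last - t_0)

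Here t_0 = 0 (pre-dose) and t_last is the actual time of the 4 h measurement. Fit the planned log-scale model to this quantity.

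A useful but optional addition is to set the parameter to missing when the 4 h value is missing, because 2-4 h is half the window. Otherwise a 0-2 h mean could be reported as a 0-4 h mean: for the first heart-rate profile, (271.25 - 132)/2 = 69.6 instead of 67.8, where 132 = (68 + 64)/2 × 2 is the 2-4 h area.

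The cost is wording in three table rows and one line of code before database lock. No data collection or design feature changes.

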17.2 Pharmacodynamic Summaries

17.2.1 Pharmacodynamic Levels

Serum Potassium

BLQ serum potassium concentrations will be set to ½ lower limit of quantification (LLOQ) in the computation of mean concentration values. Descriptive statistics (n, arithmetic mean, SD, CV%, median, min, and max,) will be used to summarize serum potassium concentrations and changes from baseline by treatment at each scheduled time point.

Participants excluded from the PD analysis set will be flagged in the listing and excluded from descriptive statistics.

All individual participant serum potassium concentrations, time deviations and comments will be listed.

Linear plots of the arithmetic mean serum potassium concentrations by scheduled sampling time will be provided by treatment (2 treatments in one plot). These plots will show time in hours. The plots will match the summary table results.

Linear spaghetti plots of serum potassium concentrations by actual sampling times will be provided by treatment.

Heart rate and QTcF

Refer to Section 18.1.5 for reporting of the heart rate and QTcF values.

17.2.2 Pharmacodynamic Parameters

PD parameters will be calculated in SAS.

Actual times, rather than scheduled sampling times, will be used in all computations involving timepoints, except for pre-dose timepoint. Pre-dose timepoints will be set to zero.

Descriptive statistics (number of participants, arithmetic mean, SD, CV, geometric mean, median, min, and max) will be used to summarize the calculated PD parameters by treatment. For Emax and Emin, only median, min and max will be presented.

Participants excluded from the PD analysis set will be flagged in the listing and excluded from descriptive statistics.

All individual participant serum potassium parameters, heart rate and QTcF parameters will be listed.

17.2.2.1 Statistical Analysis of Pharmacodynamic Parameters

Analysis will be performed to compare the PD parameters after dosing of salbutamol HFA-152a MDI and salbutamol HFA-134a MDI (currently marketed Ventolin product). Analysis will be performed on the natural logarithm of Emin and AUEC of serum potassium, and EMax and AUEC of heart rate and QTcF, using a linear mixed model with the treatment and period (dosing day) as fixed effects and subjects as random effects. A one model will be used, grouped by parameter.

Point estimates and 90% CIs for treatment differences on the log scale derived from the model will be exponentiated to obtain estimates for geometric mean (GM) ratios and CIs on the original scale. The within-subject coefficients of variation (CVw) for AUEC, Emin and Emax will be calculated based on the loge-normal distribution.

Model Checking & Diagnostics:

- Model assumptions will be checked before analysis.
- The underlying distributional assumptions involved in the statistical analyses will be assessed by visual inspection of residual plots. Normality will be examined by normal probability plots while homogeneity of variance will be assessed by plotting the residuals against the predicted values for the model.
- If the assumptions are seriously violated, then alternative data transformations will be explored. If no suitable transformation can be found, equivalent nonparametric analyses (ex. Wilcoxon signed-rank test) will be performed.

The following kernel code of SAS PROC MIXED will be used:

```
proc mixed;  
  by parameter;  
  class subject treatment period;  
  model log(value)= treatment period / ddfm=kenwardroger cl;  
  random subject /type=un;  
  lsmeans treatment period /alpha=0.1;  
  /*estimates for treatment order Test1-Ref*/  
  estimate "T vs R" treatment 1 -1 /alpha=0.1;  
run;
```

SAS code might be updated depending on the data. An unstructured type of the covariance matrices R (accounting for the within subject variability) and G (accounting for the between subject variability) will be used. If this model fails to converge, alternative covariance structures may be considered based on a lower AIC values (for example variance component, etc.). For the described linear mixed model analyses, the Kenward and Roger method for approximating the denominator degrees of freedom and correcting for bias in the estimated variance-covariance of the fixed effects will be used.

Statistical analysis model table will present N, n, least squares GM values and associated 90% CI, GM ratios and associated 90% confidence intervals and within-subject CV.

Intercurrent events and handling of missing data:

- Participant level missing PD measurements considered as missing at random, will not be imputed.
- The PD measurements will be affected by occurrence of the intercurrent event (Treatment discontinuation of the study) would be treated as missing at random from the occurrence of the intercurrent event until the end of the study and only reliable available data will be used in the primary analysis and summary descriptive.

18.0 Safety Analyses

18.1 Safety Variables

The following safety variables will be summarized:

- Adverse Events (AEs)
- Vital Signs
 - Supine Blood Pressure
 - Systolic Blood Pressure (SBP)
 - Diastolic Blood Pressure (DBP)
 - Pulse rate
- Electrocardiograms (ECG)
 - Heart Rate
 - PR Interval
 - QRS-Duration
 - QT Interval
 - QTc (Fridericia's) Interval
- Clinical Laboratory Evaluations
 - Clinical Chemistry (including glucose measurements)
 - Hematology
 - Urinalysis

Impact of COVID-19 Pandemic on Safety Results

Available safety results of participants with COVID-19 will not be excluded from any safety analysis.

No specific analyses on safety endpoints will be performed on subjects without and with COVID-19.

18.1.1 Adverse Events

All AE summaries will include only treatment emergent adverse events (TEAEs). TEAE are those which occur (or worsen) after the first dose of study drug.

TEAEs occurring following dosing in a specific period but before dosing in the next period will be attributed to that specific period. If the time is missing for an AE on a dosing day then the AE will be attributed to the treatment given on that day.

A summary overview of the number of events, and number and percentage of participants reporting TEAEs, TEAEs by severity, TEAEs by relationship, SAEs, and participants who discontinued study drug due to an AE will be provided.

A breakdown of the number of TEAEs, number and percentage of participants reporting each TEAE, categorized by body system and preferred term coded according to MedDRA (Version 25.0 or higher), will be presented by treatment and overall. One such table will be presented for all TEAEs and one such table will be presented for TEAEs considered to be related to the study medication.

Participants will only be counted once within each body system or preferred term.

The system organ class and preferred terms in these tables will be ordered by descending (total) number of participants per system organ class and within the system organ class per preferred term.

A summary of events reported, categorized by relationship not related vs related, will be provided by treatment and overall.

A summary of events reported, categorized by severity (categories as recorded in the eCRF: mild, moderate, severe) will be provided by treatment and overall. If AEs are judged as severe, the additional indication life-threatening or results in death will be combined in the summary, resulting in the following severities:

- mild
- moderate
- severe (no indication of life-threatening or fatal AE)
- life-threatening (severe AE with indication life-threatening)
- fatal (severe AE with indication results in death).

These tables will present the number of events, and number and percentage of participants per given category.

A listing of adverse events (AEs) leading to study discontinuation will be provided.

All AEs (including non-treatment-emergent events in a separate listing) recorded on the eCRF will be listed.

The following missing data will be imputed as defined (for calculations only / will not be presented):

- Missing AE start and / or end times for the calculation of onset and duration will be assumed to be at 00:01 for a start time and 23:59 for end times
- Missing AE severity or relationship will be assumed to be severe or related, respectively
- Missing AE start times for the determination of treatment emergence will be assumed to occur after treatment unless partial date documents the AE as happening prior to treatment
- Missing AE start times for the determination of treatment assignment will be assumed to occur after treatment on the recorded date one minute after dosing
- Missing AE start date: First of the month will be used unless this is before the date of first study treatment of the cohort (i.e. clinic group); in this case the date of first study treatment date will be used.
- Missing AE end date: Last day of the month will be used, unless this is after the date of last visit of the cohort (i.e. clinic group); in this case the last visit date of the cohort will be used.
- Completely missing start or end dates will remain missing, with no imputation applied. Consequently, time to onset and duration of such events will be missing.

Onset of AEs related to treatment and duration of AEs will be calculated as follows:

Onset (time since last dosing in days, hours, minutes [dd hh:mm])	AE start date/time - treatment start date/time.
Duration (in dd hh:mm)	AE end date/time – AE start date/time.

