8.11. Timing of assessments

8.11.1. Timing of dosing

The study intervention will be administered between 08:00 and 10:00 hours in the morning. Dosing for each individual participant will be at around the same time (± 1 hour) on each dosing day.

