- e. Blood sampling for serum potassium (PD) and glucose (safety): on each dosing day (Day 1 and 4), blood samples will be taken pre-dose and at the following time points post-dose: 15 and 30 minutes and 1, 1.5, 2 and 4 hours post-dose.
- f. Vital signs (systolic and diastolic blood pressure, and pulse rate): vital signs will be recorded at screening, admission, on each dosing day (Day 1 and 4) at pre-dose and at the following time points post-dose: 15 and 30 minutes and 1, 1.5, 2 and 4 hours post-dose, and at discharge.
- g. 12-lead ECG: 12-lead ECG will be recorded at screening, admission, on each dosing day (Day 1 and 4) at pre-dose and at the following time points post-dose: 15 and 30 minutes and 1, 1.5, 2 and 4 hours post-dose, and at discharge. As the ECG parameters QTc and HR will be PD parameters, ECG will be measured in triplicate at pre-dose on Days 1 and 4. The 3 pre-dose measures will be averaged for QTc interval and HR to derive one baseline value. Each individual capture of the triplicate 12-lead ECG set will be separated by 1 to 5 minutes between the first and the third ECG. Post-dose 12-lead ECG measurements will be single measurements on both dosing days. Note: if an ECG meets potential stopping criteria, then the ECG measurement should be repeated in triplicate, with the averaged QT and QTcF used to determine stopping.
- h. Participants will be trained by using the CCI device on Day -1 and prior to each dosing on Days 1 and 4. Additional training instructions are provided using the CCI device which provides auditory feedback when the participant generates an adequate breath in:
Day -1: using the CCI device, review the instructions, with particular focus on Steps 4-7. Once the participant is comfortable with using the training device, practice completing a sequence of 8 puffs.
Dosing days: using the CCI device, review the instructions, and observe the patient performing a single puff using the training device. Provide feedback as necessary until proper technique is observed before conducting the full dose using the investigational inhaler.
Additional training using the CCI (eg, on Day 3) may be performed at the discretion of the clinic.
- i. Administration of study intervention: start of the 8 inhalations study intervention, with the inhalations administered at 20-second intervals. Note: All post-dose time points will be from start of dosing (first inhalation).

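### SAP 18.1.1 gives a dosing-day AE with no start time two different start times, so its derived onset conflicts with its treatment attribution

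*SAP*

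**What the plan says.** SAP 18.1.1 has three rules for an AE whose start time is missing, each for its own purpose:

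- **Onset and duration:** the missing time "will be assumed to be at 00:01 for a start time and 23:59 for end times".
- **Treatment emergence:** "Missing AE start times for the determination of treatment emergence will be assumed to occur after treatment unless partial date documents the AE as happening" before it.
- **Treatment assignment:** the start "will be assumed to occur after treatment on the recorded date one minute after dosing". The text earlier in the section agrees: "If the time is missing for an AE on a dosing day then the AE will be attributed to the treatment given on that day".

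Onset is described as the time elapsed since the last dosing and is computed as "AE start date/time - treatment start date/time". Duration is AE end minus AE start. A start date with a missing day goes to the first of the month, or to the clinic group's first treatment date if that is later. This floor works on dates only; nothing similar applies to times.

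Protocol 8.11.1 fixes the clock time of dosing: "The study intervention will be administered between 08:00 and 10:00 hours in the morning". The dosing days are Days 1 and 4 (SAP Appendix 2). The lead-in to the imputation list in SAP 18.1.1 says that imputed values serve calculation and are not shown. SAP 9.1.2 adds that listings show partial dates as they were captured.

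**The concern.** An AE has one start. The SAP places it just after midnight when it computes how long after dosing the event began, and just after the dose when it decides which treatment the event belongs to. With morning dosing these times are hours apart and lie on opposite sides of the dose. The derived onset can then say that the event came before the treatment to which the same section assigns it.

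On Day 1 the midnight start also conflicts with the collection rule. Protocol 8.4.1 collects AEs only from the start of study intervention and sends earlier occurrences to medical history. SAEs are the exception, since they are collected from consent. A non-serious Day 1 AE therefore cannot have begun at 00:01.

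At stake is the correctness of two variables that the SAP defines, onset and duration, in the few records where the rule applies.

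**Working it through.** The documents give no onset figure to reproduce, so the check applies the SAP's own formulas.

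**Inputs**
- Imputed start for onset and duration: 00:01 (SAP 18.1.1)
- Imputed start for assignment: dose time + 1 min (SAP 18.1.1)
- Dose time: 08:00 to 10:00 (Protocol 8.11.1)
- Dosing days: 1 and 4 (SAP Appendix 2)

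**Day 1 AE, start time missing.** Onset = AE start - treatment start.
- Dose at 08:00: 00:01 - 08:00 = -7 h 59 min
- Dose at 09:00: 00:01 - 09:00 = -8 h 59 min
- Dose at 10:00: 00:01 - 10:00 = -9 h 59 min

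Under the assignment rule the same event starts 1 min after the dose.

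**Day 4 AE, start time missing.** The result depends on which dose counts as the last one.
- Measured from the Day 4 dose: again -7 h 59 min to -9 h 59 min.
- Last dose judged from the imputed 00:01 on Day 4: the Day 4 dose has not yet been given, so the reference is the Day 1 dose. Three days are 72 h, so onset is 72 h - 7 h 59 min = +64 h 01 min for a Day 1 dose at 08:00, and 72 h - 9 h 59 min = +62 h 01 min for one at 10:00.

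The second reading gives a positive onset, but it counts from the other treatment of the crossover while the event is attributed to the Day 4 treatment. Both readings conflict with the attribution.

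**Duration.** The gap between the two imputed starts is (dose + 1 min) - 00:01.
- Dose at 08:00: 08:01 - 00:01 = 8 h 00 min
- Dose at 10:00: 10:01 - 00:01 = 10 h 00 min

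For an event with start and end times both missing on one dosing day, the SAP rule gives 23:59 - 00:01 = 23 h 58 min. From the assignment time it would be 15 h 58 min (08:00 dose) or 13 h 58 min (10:00 dose).

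**Second route to the same result.** If a start date lacks the day and is moved to the first treatment date, and the time is missing too, the event lands on that date at 00:01. Onset is again negative for anyone dosed that morning.

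**Non-dosing days.** On Day 2 a start at 00:01 gives 24 h - 7 h 59 min = 16 h 01 min (08:00 dose) or 24 h - 9 h 59 min = 14 h 01 min (10:00 dose). Onset is positive and agrees with the attribution, so 00:01 does no harm there.

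**The case against.** The strongest reply is that nothing reported depends on this. A reader might infer that the AE listing will show events starting 8 to 10 h before the dose. The documents do not support that: imputed times are not presented (SAP 18.1.1) and partial dates appear as captured (SAP 9.1.2). Only the derived onset or duration could show the anomaly. The SAP does not say where these are displayed, and the table shells are a separate document (SAP 9.5).

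Nor are TEAE counts or treatment comparisons distorted. Emergence and assignment have their own rules, and planned Tables 15.4.1.1 to 15.4.1.8 name neither onset nor duration. Causality is not at risk either: the investigator judges it for each event (Protocol 10.3.6.3), and a missing relationship is set to related (SAP 18.1.1).

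It would also go too far to say that every dosing-day AE with a missing time gets a negative onset, or that each duration is known to be overstated. On Day 4 the sign depends on the reading of *last dosing*. A true start before the Day 4 dose is also possible, because the participant was already dosed on Day 1. The interval from 00:01 to 23:59 is the longest that the recorded dates allow, and dose plus one minute is an assumption too.

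All of this stands and limits the point. It does not remove it. SAP 18.1.1 defines onset and duration as calculated variables, and ADAE is among the datasets delivered to the sponsor (SAP 9.2.5). For a non-serious Day 1 AE the derived onset cannot be right under the protocol's own collection rule.

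**Conclusion.** The point holds, and it is minor. For a Day 1 AE with no start time, the stated rules give a derived onset of about -8 to -10 h for an event that the same section treats as post-dose. For a Day 4 AE they give either that value or about +62 to +64 h from the dose of the other treatment, and each is inconsistent with the attribution. Duration is 8 to 10 h longer than it would be from the SAP's own assignment time.

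This rests on dosing within the protocol's 08:00 to 10:00 window and on the onset formula being programmed as written, with no unstated floor at dose time. The documents do not say how many AEs will lack a start time. The assumption here is that there will be few, because participants are confined throughout the intervention period. The effect is confined to derived onset and duration for those events.

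**What to change.** Replace the first imputation rule in SAP 18.1.1 with one start-time rule for dosing days:

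- For an AE dated on a dosing day (including a date moved to the first treatment date), with a missing start time and treated as post-dose, use dose time + 1 min for onset, duration and attribution alike.
- Measure onset from the dose to which the AE is attributed. This settles the Day 4 ambiguity.
- Keep 00:01 on non-dosing days.
- Keep 00:01 also where a recorded end time precedes that day's dose, and attribute that AE to the previous period. Without this exception the new rule would give a negative duration. On Day 1 there is no previous period, and Protocol 8.4.1 would class a non-serious occurrence of this kind as medical history.

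Under this rule, onset for the affected post-dose events is 1 min whatever the dose time. That is a nominal value and could look like an immediate reaction, so flag these records as imputed. The cost is one or two SAP sentences and a small change to the ADAE derivation. Attribution changes only for an AE with a recorded end before the Day 4 dose.
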